- Patients on Medicare Advantage or HMO plans cannot be analyzed because Medicare data do not contain comprehensive claims records for these patients, who make up 32% to 42% of the Medicare population, with higher uptake in certain geographic regions, potentially affecting generalizability of our findings.
- The planned survival analysis will be based on an intent-to-treat approach, regardless of changes to their exposure status during the follow-up, which may influence the survival outcome.
- Because the treatment regimens will be defined using a claims-based algorithm, it is reasonable to assume some risk of misclassification—even though the algorithm rules will be drawn from previously published methods.

The SEER-Medicare database used for this study, however, remains a unique—and the most authoritative—data source to examine survival outcomes in older patients with diagnosis of cancer at the US Medicare population level.

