The SEER-Medicare database is composed of 2 large population-based sources of data that provide detailed information about Medicare beneficiaries with cancer: (1) the SEER registry data that contain information about an incident cancer diagnosis and (2) linked Medicare data that contain longitudinal information on Medicare enrollment and

specific healthcare services received in different settings (e.g., hospitals, physician offices, outpatient clinics, nursing homes), as well as prescription drug utilization. The linkage of these 2 data sources results in a unique source of information that can be used for an array of epidemiological research, including health services use and survival outcomes, among older patients with cancer in the United States (US) Medicare population.

The SEER registries are part of the SEER Program, which is an epidemiologic surveillance system consisting of population-based tumor registries in certain states and metropolitan areas designed to track cancer incidence and survival in the US. The SEER registries collect information on nearly all (98%) newly diagnosed cancer cases, including breast cancer, in persons residing in SEER areas. SEER areas have been shown to be nationally representative (Nattinger et al., 1997) and the 21 registries represented in the SEER data linkage available for this study (SEER-21) capture over one-third (35%) of the total US population (Enewold et al., 2020). In contrast to the entire population of the US, the SEER Program encompasses a population that displays greater racial and ethnic diversity, along with a higher representation of individuals facing economic disadvantages (Enewold et al., 2020).

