Geographic region	Demographics (assessed at mBC diagnosis)	
The geographic region of patients' county of residence will be defined according to the rural-urban continuum code (version year 2013) and categorized as follows:
 
 • Big metro: Counties in metropolitan areas ≥ 1 million population • Metro: Counties in metropolitan areas of 250,000 to 1 million population • Urban: Counties in metropolitan areas of < 250,000 population • Less urban: Nonmetropolitan counties adjacent to a metropolitan area • Rural: Nonmetropolitan counties not adjacent to a metropolitan area 
These categories may be further combined for statistical purposes as below:
 
 • Large urban (big metro and metro areas) • Small urban (urban and less urban areas) • Rural

Variable	Role/objective	Definition
Household income	Demographics (assessed using the latest available ACS data: 2008-2012)	The median household income based on patients' census tract of residence will be defined according to American Community Survey data (2008-2012). Data will be categorized using quartile distribution as follows: 
 • Quartile 1 (e.g., < \$55,000) • Quartile 2 (e.g., \$55,000-\$64,999) • Quartile 3 (e.g., \$65,000-\$74,999) • Quartile 4 (e.g., \$75,000+) • Missing/unknown
LIS coverage	Demographics (assessed during 6 months before index date)	Patient's enrollment in an LIS plan during the 6-month baseline period will be assessed and summarized as a binary variable: 
 • Any LIS coverage • No LIS coverage
Medicaid (dual) eligibility	Demographics (assessed as available in the data at mBC diagnosis or treatment) [Not to be used in propensity score model]	Medicare with Medicaid (dual) eligibility status will be summarized according to primary payer/insurance carrier at the time of initial diagnosis and/or treatment at the reporting facility: 
 • Medicaid • No Medicaid

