7.2 STATISTICAL ANALYSES

7.3 ANALYSES FOR PRIMARY OBJECTIVE

For the primary objective, the association between primary independent variable (treatment type: palbociclib + AI or AI alone) and the outcome variable (OS) will be assessed using unadjusted Kaplan-Meier analysis and multivariable methods. The primary method of analysis to account for observed confounders will be stabilized inverse probability of treatment weighting (sIPTW). Additionally, as sensitivity analyses, multivariable Cox proportional hazards (CPH) regression and propensity score matching (PSM) will be performed. *Both IPTW and PSM are propensity score (PS)-based methods commonly used to achieve balance between treatment and control groups in retrospective cohort study designs.* All methods are described below in detail.

Kaplan-Meier Analysis

Time-to-event outcome (i.e., OS) will be described using unadjusted Kaplan-Meier analyses; median time-to-event (in months) and landmark probabilities of event at various timepoints (e.g., 12 months, 24 months) will be estimated, along with 95% CIs and log-rank *P* values. Graphical displays of the data will also be generated as appropriate. Kaplan-Meier analysis may also be performed using the stabilized weights or among the PS-matched groups (see details in this section below), and the weighted or PS-matched survival curves may be drawn.

Cox Proportional Hazards Regression

The CPH regression model may be used to estimate a hazard ratio of the OS, along with 95% CI, for the primary exposure—a dichotomous variable indicating whether the patient received AI + palbociclib versus AI alone—and for each of the control variables included in the model, indicating higher or lower rate of death (relative to a reference category) at any given point in time after the index date. The patient demographic and clinical characteristics that will be considered for confounding adjustment in the model are described earlier in [Table 5-2](#).

Propensity Score Estimation

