As the first step in implementation of PS-based methods (IPTW and PSM), the PS (i.e., the estimated probability of treatment assignment) will be obtained from a logistic regression model where the treatment assignment (treatment vs. control) will be regressed on a set of covariates or confounders. The baseline covariates or control variables that will be considered for adjustment in the multivariable logistic regression for deriving treatment probabilities (i.e., PSs for IPTW and PSM) are described earlier in [Table 5-2](#). The following variables will be included in the model: age group, race, year of mBC diagnosis, marital status, geographic status of residence, median household income, LIS coverage, tumor grade at initial diagnosis, involvement of metastatic sites at initial diagnosis (bone, brain, liver, and lung as independent binary variables), and NCICI score category. If any covariates are identified to have missing data, they may be coded as “missing” or “unknown” and included as categorical variables in the model.

Covariate Balancing

The following process will be implemented to determine whether there is sufficient overlap between the patient populations of the 2 treatment cohorts:

- Compute the standardized mean difference in PS for each level of each baseline covariate
- Graphically assess differences in the full distribution of each covariate between 2 treatment cohorts
- An absolute standardized mean difference < 0.1 indicates negligible difference and is considered a good balance

Covariate balance will be examined using both IPTW and PSM techniques as described below. Subsequently, depending on the quality of balance, the endpoint (OS) may be assessed using one or both techniques (Austin, 2014; Buchanan et al., 2014).

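### The covariate called Geographic region records urbanicity, not location, so any registry differences in both palbociclib uptake and survival would be neither balanced nor detected

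*SAP*

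**What the plan says.** SAP section 5.5, Table 5-2, contains a covariate labelled Geographic region. Its definition is that the patient's "county of residence will be defined according to the rural-urban continuum code (version year 2013) and categorized as follows". The top level is "Big metro: Counties in metropolitan areas ≥ 1 million population", wherever in the country that county lies. Two further metropolitan levels depend on population, and two nonmetropolitan levels depend on adjacency to a metropolitan area. The five levels may be collapsed to three, again without location. Table 1 of the protocol has the same definition.

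SAP section 2.1 states that "the 21 registries represented in the SEER data linkage available for this study (SEER-21) capture over one-third (35%) of the total US population".

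SAP section 7.3 sets the main method: "The primary method of analysis to account for observed confounders will be stabilized inverse probability of treatment weighting (sIPTW"). It names the propensity-score variables one by one. The place-related terms are "geographic status of residence, median household income, LIS coverage", where the first is the rural-urban variable, the second a census-tract measure and the third a subsidy indicator.

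Protocol section 9.9 mentions regional variation once, for Medicare Advantage and HMO plans, which hold 32% to 42% of the Medicare population, "with higher uptake in certain geographic regions, potentially affecting generalizability of our findings".

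**The concern.** A reader who sees Geographic region in the covariate table may assume that location has been adjusted for. It has not. A patient in a large metropolitan county of one state is coded identically to a patient in a large metropolitan county of any other state.

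Registry is the nearest thing this study has to a site. If places that took up palbociclib faster in 2015-2019 also had different background mortality, after allowing for the listed covariates, the hazard ratio would attribute part of that difference to the drug. Year of diagnosis adjusts for the common time trend in adoption, but not for places adopting at different speeds. The stake is a shift in the primary hazard ratio that no planned analysis is set up to show, in a study that tests superiority against a hazard ratio of 1 or more (SAP section 3).

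**Working it through.** **Step 1: trace the variable through the plan.** The documents give no figure to reproduce here: Protocol section 9.5 states no sample size, event count or power. The check is whether location enters any analysis.

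- Table 5-2: rural-urban code and census-tract income; no registry, state or census region.
- Propensity score (SAP 7.3): a fixed list whose only geographic category is the rural-urban variable.
- Balance check (SAP 7.3): standardized mean differences (SMDs) for the baseline covariates, with an absolute value below 0.1 taken as good. Registry is not among them, so its balance is never tabulated. The option to adjust for residual imbalance cannot act on a variable that is not tabulated.
- Matching uses the same propensity score; the Cox model draws on the same Table 5-2.
- Sensitivity analyses (SAP 7.6): none uses location.
- Subgroups (SAP 4.4 and 7.5): none named by location. An open clause on other patient characteristics would permit one, but it is optional and is not a check for confounding.
- Limitations (Protocol 9.9): performance status, laboratory results and mutations are given as examples of unmeasured confounders. Region is not mentioned there.

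**Step 2: illustrate the size.** Every input here is an assumption: true treatment hazard ratio 1.0; half of patients in low-uptake and half in high-uptake registries; uptake 35% vs 55%, or 30% vs 60%; mortality ratio m (low-uptake relative to high-uptake) of 1.1 to 1.3, independent of the covariates already adjusted.

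Share of each arm from low-uptake registries, by Bayes' rule:

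- 35% vs 55%: palbociclib p1 = 0.35/(0.35 + 0.55) = 0.389; AI alone p0 = 0.65/(0.65 + 0.45) = 0.591.
- 30% vs 60%: p1 = 0.30/0.90 = 0.333; p0 = 0.70/1.10 = 0.636.

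Bias factor for an omitted binary confounder: B = [1 + (m − 1)p1] / [1 + (m − 1)p0].

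| Uptake | m | B by formula | Simulated Cox HR |
|---|---|---|---|
| 35% vs 55% | 1.1 | 1.0389/1.0591 = 0.981 | 0.983 |
| 35% vs 55% | 1.3 | 1.1167/1.1773 = 0.949 | 0.947 |
| 30% vs 60% | 1.1 | 1.0333/1.0636 = 0.972 | 0.972 |
| 30% vs 60% | 1.3 | 1.1000/1.1909 = 0.924 | 0.916 |

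If high-uptake registries carry the higher mortality instead, the shares become 0.611 and 0.409, or 0.667 and 0.364. The factor then runs from (1 + 0.1 × 0.611)/(1 + 0.1 × 0.409) = 1.02 to (1 + 0.3 × 0.667)/(1 + 0.3 × 0.364) = 1.08. If registries do not differ in uptake, or do not differ in survival, B = 1.

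**Step 3: a wider range.** Uptake gaps of 10 to 30 points, with a death hazard ratio of high- versus low-uptake registries from 0.95 down to 0.70, give B from 0.995 to 0.898. Cox simulations with 200,000 patients gave 0.954 (formula 0.956) and 0.893 (formula 0.898) for two of these settings. Adding the registry group to the model returned 0.997 and 0.998.

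**Step 4: would the plan's own rule notice?** SMD = |p1 − p0| / √{[p1(1 − p1) + p0(1 − p0)]/2}. For gaps of 10, 20 and 30 points it is 0.20, 0.41 and 0.64 before weighting. All exceed 0.1, and none would appear in the balance table.

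**Step 5: scale against the cited results.** The randomized first-line hazard ratio cited in SAP section 2 is 0.956, so shifts of 0.98 to 0.92 are of the same order. The cited electronic-health-record study of palbociclib plus AI reports 0.76 (0.65 to 0.87). Dividing by the most extreme factor gives 0.76/0.898 = 0.846 and an upper limit of 0.87/0.898 = 0.969, still below 1.

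**The case against.** The strongest case against is that this is an omission of unknown consequence. Neither document reports registry-level palbociclib uptake or survival. A reader might infer that the registries do differ and that the hazard ratio is biased in palbociclib's favour; the documents support neither step. A reader might also take the uptake remark in Protocol 9.9 as evidence of regional prescribing. It concerns Medicare Advantage and HMO enrolment, and the corresponding inclusion criteria apply to both arms alike. Treating that as a generalizability limit is reasonable, and it does not show confounding. These objections stand, and they limit the point to what could go unseen.

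Several pathways are also partly covered. Age group, race, grade (with an unknown level), four metastatic sites and comorbidity category address case mix; subsidy coverage, income and rural-urban level address access; year addresses calendar change. This makes the illustration closer to a ceiling than an expectation, because it assumes regional mortality independent of all these. It does not show that registries end up balanced, and the plan never checks.

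Finally, if region affects prescribing but not survival, adding it to the propensity score can widen the interval and amplify bias from unmeasured confounders such as performance status. That is a real cost, and the reason to show results both ways. The return to 1.00 in the simulations holds because the simulated grouping was itself the confounder. Census region would leave differences between registries within a region unadjusted.

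**Conclusion.** The gap is confirmed in both documents: the covariate called Geographic region carries no location, and no planned analysis includes registry, state or census region. Any registry differences in both uptake and survival, beyond what urbanicity, income, subsidy coverage, race, year and the clinical covariates capture, would be neither balanced nor detected. Size and direction are unknown. Under the stated assumptions the hazard ratio would move from 1.0 to about 0.98 to 0.92, or to about 1.02 to 1.08 if the pattern reverses. The documents do not support the stronger conclusion that the primary result will be biased. Within the assumed range, this source alone would not take the upper limit of the cited real-world estimate above 1. It is a moderate specification gap, worth closing because closing it is cheap.

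**What to change.** In SAP Table 5-2:

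- Relabel the present variable *urbanicity*.
- Add US census region, derived from registry or county of residence.

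In SAP sections 7.3 and 7.6:

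- Add region to the balance table under the existing SMD limit of 0.1.
- Include region in the propensity score and the Cox covariates.
- Report the sIPTW hazard ratio with and without region, stating in advance that the version with region is primary.
- Add one sensitivity analysis: the weighted Cox model stratified by region.

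The cost is SAP wording and one derived variable. Protocol section 9.7.1 already leaves the final covariate list to the SAP before final analysis. The documents do not expressly list a registry identifier among the fields, but the plan already uses county of residence, so a coarse region should be obtainable; this should be confirmed. Four regions add about three parameters, against 20 for all 21 registries, whose feasibility cannot be judged without a sample size. The downsides are a slightly wider interval, or some amplification of unmeasured confounding, if region affects prescribing but not survival. Differences between registries within a region would remain unadjusted.

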6 HANDLING OF MISSING VALUES

No imputation for missing values will be performed. Number and percentage of patients with missing data on all key study measures will be reported.

7 STATISTICAL METHODOLOGY AND STATISTICAL ANALYSES

7.1 STATISTICAL METHODS

Means with standard deviations, medians with interquartile range, and min/max values will be provided for continuous variables when performing descriptive analysis of continuous data. Numbers and percentages will be provided for dichotomous and polychotomous variables when performing descriptive analysis of categorical data. Baseline patient demographics (e.g., age, race, marital status) and clinical characteristics (e.g., metastatic sites, NCICI) will be descriptively analyzed and reported. Unadjusted and/or weighted Kaplan-Meier curves will be drawn to illustrate time-to-event endpoints.

All analyses will be performed separately for the primary and exploratory objectives described in Section 2.2, and any computations and generation of tables, listings, and data for figures will be conducted using SAS statistical software, version 9.4 or later (SAS Institute; Cary, North Carolina).

7.2 STATISTICAL ANALYSES

7.3 ANALYSES FOR PRIMARY OBJECTIVE

For the primary objective, the association between primary independent variable (treatment type: palbociclib + AI or AI alone) and the outcome variable (OS) will be assessed using unadjusted Kaplan-Meier analysis and multivariable methods. The primary method of analysis to account for observed confounders will be stabilized inverse probability of treatment weighting (sIPTW). Additionally, as sensitivity analyses, multivariable Cox proportional hazards (CPH) regression and propensity score matching (PSM) will be performed. *Both IPTW and PSM are propensity score (PS)-based methods commonly used to achieve balance between treatment and control groups in retrospective cohort study designs.* All methods are described below in detail.

Kaplan-Meier Analysis

Time-to-event outcome (i.e., OS) will be described using unadjusted Kaplan-Meier analyses; median time-to-event (in months) and landmark probabilities of event at various timepoints (e.g., 12 months, 24 months) will be estimated, along with 95% CIs and log-rank *P* values. Graphical displays of the data will also be generated as appropriate. Kaplan-Meier analysis may also be performed using the stabilized weights or among the PS-matched groups (see details in this section below), and the weighted or PS-matched survival curves may be drawn.

Cox Proportional Hazards Regression

The CPH regression model may be used to estimate a hazard ratio of the OS, along with 95% CI, for the primary exposure—a dichotomous variable indicating whether the patient received AI + palbociclib versus AI alone—and for each of the control variables included in the model, indicating higher or lower rate of death (relative to a reference category) at any given point in time after the index date. The patient demographic and clinical characteristics that will be considered for confounding adjustment in the model are described earlier in [Table 5-2](#).

Propensity Score Estimation

As the first step in implementation of PS-based methods (IPTW and PSM), the PS (i.e., the estimated probability of treatment assignment) will be obtained from a logistic regression model where the treatment assignment (treatment vs. control) will be regressed on a set of covariates or confounders. The baseline covariates or control variables that will be considered for adjustment in the multivariable logistic regression for deriving treatment probabilities (i.e., PSs for IPTW and PSM) are described earlier in [Table 5-2](#). The following variables will be included in the model: age group, race, year of mBC diagnosis, marital status, geographic status of residence, median household income, LIS coverage, tumor grade at initial diagnosis, involvement of metastatic sites at initial diagnosis (bone, brain, liver, and lung as independent binary variables), and NCICI score category. If any covariates are identified to have missing data, they may be coded as “missing” or “unknown” and included as categorical variables in the model.

Covariate Balancing

The following process will be implemented to determine whether there is sufficient overlap between the patient populations of the 2 treatment cohorts:

- Compute the standardized mean difference in PS for each level of each baseline covariate
- Graphically assess differences in the full distribution of each covariate between 2 treatment cohorts
- An absolute standardized mean difference < 0.1 indicates negligible difference and is considered a good balance

Covariate balance will be examined using both IPTW and PSM techniques as described below. Subsequently, depending on the quality of balance, the endpoint (OS) may be assessed using one or both techniques (Austin, 2014; Buchanan et al., 2014).

IPTW: The general approach for an IPTW analysis involves calculating the inverse probability weights and then using these weights to estimate the treatment effect. The IPTW for each patient is the inverse of their PS for their respective treatment group. For exposed individuals, the weight is $1/PS$, and for unexposed individuals, it is $1/(1 - PS)$. The treatment weights derived from the PSs might be large because patients receiving palbociclib + AI treatment may have PSs closer to 0, while patients receiving AI monotherapy may have scores closer to 1. Consequently, extreme weights and inflated variance can occur. To mitigate this potential problem, we will calculate sIPTW, as suggested by Pezzi et al. (2016), Xu et al. (2010), and Shiba and Kawahara (2021). By employing sIPTW, the point estimates of the treatment effect will remain unaffected compared with unstabilized weights while leading to a more accurate estimation of the variance. Once the stabilized inverse probability weights are calculated for each individual, they will be used to estimate the average treatment effect by comparing the weighted outcomes between the treatment (palbociclib + AI) and control (AI alone) groups. For Kaplan-Meier analysis, sIPTW will be applied to assess weighted median OS and 95% CI; weighted survival curves will be drawn and weighted landmark probabilities of event at various timepoints will be estimated (e.g., 12 months and 24 months). For assessing weighted estimate of hazard ratio for the treatment type (AI + palbociclib vs. AI alone), sIPTW will be applied to the Cox proportional hazards model. Variance will be estimated using robust variance estimation method to account for the weighted nature of the data. Point estimate (i.e., hazard ratio) will be derived along with 95% CI; any covariates with residual imbalance may be adjusted for in this step.

PSM: In the PSM technique, each patient in the palbociclib +AI cohort will be matched to a patient in the AI alone cohort using a 1-to-1 matching with no replacement, using the nearest neighbor method to match by closest propensity scores (with a caliper of 0.01). As described above, median OS, landmark probabilities of event at various timepoints, and 95% CI for the matched cohorts will be assessed, and the hazard ratio will be assessed using the univariate CPH model. To plot survival functions and to test for differences between AI + palbociclib and AI alone, the Kaplan-Meier estimator will be used. Given the matched nature of the study cohorts, the CPH analysis will use a robust variance estimator to account for the clustering within paired sets.

All patients will be followed from the start of therapy line through the earliest of the following: death; disenrollment from Medicare Parts A, B, or D; enrollment in an HMO plan; or end of the study database (31 December 2020). Section 7.6 discusses potential sensitivity analyses (e.g., adjusting for subsequent treatments received).

